### **6.3 Day 2-Week 4**

Participants will consume coded capsules of either LT4 or LT3 supplements as divided doses three times per day in the morning, afternoon, and evening.

### **6.4 Medication Titration (Q4Weeks)**

Participants will have TSH testing every 4 weeks (acceptable range 4-8 weeks) at a Penn outpatient laboratory facility until TSH is at goal, and then the participant will be scheduled for Visit 2. This visit can be scheduled up to four weeks from the date of the last TSH level.

Symptoms of palpitations and shortness of breath will be ascertained at the reminder calls prior to TSH level checks. The total daily dose of study medications will be adjusted by blinded study investigators to a TSH of 0.5-1.5 mU/L. New study medication for adjustment dosing will be mailed overnight to participants within 5 days of receipt of the interim lab results. Once the TSH is at goal, an activity and heart rate monitor will be mailed to the participant to wear one week prior to the next study visit.

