**Figure 4**

All study visits will be at the University of Pennsylvania's Clinical and Translational Research Center (CTR). There will be a screening visit (Day -60 to Day -1), a baseline

CONFIDENTIAL

This material is the property of the University of Pennsylvania. Do not disclose or use except as authorized in writing by the study sponsor

study visit (Visit 1; Day 1), and a final study visit while taking their first thyroid preparation (Visit 2). Following the completion of Visit 2, participants will cross-over to the second thyroid preparation and complete Visit 3, as above.

On Day 1 (baseline study visit, Visit 1) the participants will undergo their first TRH stimulation test and receive written instruction on thyroid hormone dosing by a study team member. The participant will begin oral thyroid supplementation as divided doses three times per day for four weeks starting the morning after the baseline study visit. After four weeks, the participants will have their TSH level checked at a Penn outpatient laboratory, after which LT4 or LT3 will be titrated to a target TSH level of 0.5-1.5 mU/L by a blinded study investigator. TSH levels will continue to be checked at four-week intervals until the TSH level is at goal, after which, Visit 2 will be scheduled. At Visit 2, a TRH stimulation test will be performed and participants will cross-over to the other thyroid preparation. The sequence of TSH assessment and thyroid preparation titration will occur with this thyroid preparation. At Visit 3, a TRH stimulation test will be performed and the participant will complete the study. Physiologic endpoints will be measured at each study visit.

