### 5.4 Preparation and Administration of Study Drug

TRH in powder form must be stored at -20 degrees Celsius or cooler. LT4 and LT3 must be stored at room temperature. Storage, preparation, labeling and dispensing of all study drugs (TRH, LT4, and LT3) will be done by the IDS (available at [contact] or, for after-hours emergencies, [contact]) in accordance with HUP's Pharmacy Policy and

CONFIDENTIAL

This material is the property of the University of Pennsylvania. Do not disclose or use except as authorized in writing by the study sponsor

Procedures. Each drug label will include the subject's unique identification number, date dispensed, and directions for use.

One prefilled syringe containing 200 µg TRH will be administered to participants by a CTRC nurse in the CTRC at each study visit.

TRH should be administered with the patient in the supine position. It will be administered as an intravenous bolus over 1 minute. The patient should remain supine until all of the post-injection blood draws have been completed. The patient should urinate prior to the procedure as they may feel an urge to urinate after the TRH is administered.

The LT4 and LT3 will be packaged in identical coded dose-tailored capsules containing either LT4 or LT3. The participants will be given sufficient study medication for 6 weeks at the start of each treatment regimen (LT4 or LT3). Participants will obtain TSH level checks at 4-week intervals, after which they will be provided with additional study medication as needed. If a dose change is required, new study medication will be mailed overnight to participants within 5 days of review of the lab results. Unused capsules will be returned to IDS at Visits 2 and 3.

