### **6.5 Visit 2**

Participants will repeat all measures from Visit 1 at this study visit on their first thyroid preparation (LT4 or LT3). Subjects will stop taking study drug for 4 weeks after the study visit 2. During this wash-out period once every two weeks a phone contact will continue to be made by one of the study team members to inquire if the participant has experienced any adverse events. Specifically, the participant will be asked if they have any symptoms

CONFIDENTIAL

This material is the property of the University of Pennsylvania. Do not disclose or use except as authorized in writing by the study sponsor

of palpitations or shortness of breath. A six week supply of crossover study drug will either be sent home with the participant from study visit 2 or it will be mailed to them. Subjects will be instructed to begin this study drug 4 weeks after study visit 2. TSH level will be checked 4 weeks after starting the new study drug, and all study procedures for medication titration and TSH checks will be repeated as above.

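### The six-week starting supply and the 4-8 week TSH window do not match: a late but in-window first titration TSH could be drawn up to 14 days after the capsules end

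*Combined protocol and SAP*

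**What the plan says.** **Timing of the TSH check.** Section 6.4 reads: "Participants will have TSH testing every 4 weeks (acceptable range 4-8 weeks) at a Penn outpatient laboratory facility". This is the only place where the 4-8 week range appears. Section 3.1 is narrower for the first check of period 1, "After four weeks, the participants will have their TSH level checked at a Penn outpatient laboratory", and for those that follow, "TSH levels will continue to be checked at four-week intervals until the TSH level is at goal". For period 2, Section 6.5 says "TSH level will be checked 4 weeks after starting the new study drug", and Section 5.2 agrees. Section 6.3 is headed as running from Day 2 to Week 4.

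**Starting supply.** Sections 5.2, 5.4 and 6.2 give six weeks of medication at the start of period 1. For period 2, Section 6.5 says "A six week supply of crossover study drug will either be sent home with the participant from study visit 2", or that it will be mailed.

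**Resupply.** Section 5.4 puts it after the check: "Participants will obtain TSH level checks at 4-week intervals, after which they will be provided with additional study medication as needed". Section 6.4 ties changed doses to the result: "New study medication for adjustment dosing will be mailed overnight to participants within 5 days of receipt of the interim lab results". No section provides for a refill before a late first check, and none forbids one.

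**The concern.** The titration TSH selects the next dose step from the tables in Section 5.2. The tables assume that the value was measured on drug. If the first check of a period is taken late in the accepted window, the capsules may already have run out, and the TSH would then be partly a withdrawal value.

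LT4 and LT3 clear at very different rates, so the distortion would differ between the two preparations being compared. The investigator who adjusts the dose does not know which drug the participant takes. The practical consequences would be an unneeded or larger dose increase in a participant aged 70 or older, and a longer titration with at least one more check.

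**Working it through.** The plan gives no figure of its own for this gap, so there is nothing to reproduce first. The check is calendar arithmetic on its stated numbers.

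**Inputs**
- Starting supply: 6 weeks = 42 days. At one capsule three times daily, 42 × 3 = 126 capsules (Sections 5.2, 5.4, 6.2, 6.5).
- Accepted window: 4-8 weeks = days 28-56 (Section 6.4).
- Result in under 1 day (Section 6.8); mailing within 5 days, then overnight delivery (Section 6.4).
- First dose on the morning after Visit 1 (Section 3.1).
- Half-lives: LT4 6-8 days, LT3 1-2 days (Section 1.2).
- Assumptions: every dose taken, exactly 42 days supplied, no interim refill.

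**1. Days off drug at the first draw** = max(0, draw day − 42), counted from the first dose.
- Week 4: 0. Week 6: 0.
- Week 7: 49 − 42 = 7.
- Week 8: 56 − 42 = 14.

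If the eight weeks of period 1 run from Visit 1, the last in-window draw is 55 days after the first dose, and 55 − 42 = 13. Section 6.5 counts the period 2 check from starting the drug, so 14 applies there.

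**2. On-time check.** 28 + 1 + 5 + 1 = day 35, which leaves 42 − 35 = 7 days of capsules in hand. There is no gap on the four-week schedule.

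**3. Drug remaining** = 0.5^(days off ÷ half-life).

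| Days off | LT4 (6 to 8 d) | LT3 (1 to 2 d) |
|---|---|---|
| 7 | 0.445 to 0.545 | 0.008 to 0.088 |
| 14 | 0.198 to 0.297 | 0.00006 to 0.008 |

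This is drug remaining, not TSH shift. The documents give no way to turn one into the other.

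**4. What a misread TSH could select** (Section 5.2 tables).
- *Truly at goal, read as above goal:* LT4 step 0.10 to 0.25 mcg/kg/day; LT3 step 0.03 to 0.08. Against the period 1 starting doses this is 0.10/0.7 = 14% to 0.25/0.7 = 36% for LT4, and 0.03/0.23 = 13% to 0.08/0.23 = 35% for LT3.
- *Truly above goal, read one row too high:* the error is only the difference between rows. For LT4 this is 0.25 − 0.21 = 0.04, 0.21 − 0.17 = 0.04 or 0.17 − 0.10 = 0.07 mcg/kg/day, that is 6-10% of 0.7. The largest possible row error is 0.25 − 0.10 = 0.15 (21%).
- *Already above 4.50:* no error, because the top row applies either way.

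**5. Which case applies when.** Participants enter period 1 with a TSH of at least 4.5 mU/L (Section 4.1) and a starting dose that Section 1.5 calls conservative, so most would probably still be above goal at the first check. In period 2 they start at the dose equivalent to the one held at Visit 2 (Section 5.2), so a participant truly at goal is more likely. That is where an unneeded step is most plausible. The percentages in step 4 use the period 1 starting dose and do not carry over to period 2.

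**The case against.** The strongest reply is that the specific text governs. Sections 3.1, 5.2 and 6.5 fix the first check at four weeks, and the six-week supply is that schedule plus a two-week buffer. On this reading the 4-8 week range is a general tolerance in a section headed as four-weekly. The reading is reasonable, but Section 6.4 states the range without exempting the first check, so a week-8 first draw can still be read as in window.

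The second reply is that the main harm is already addressed. Section 5.5 passes self-reported adherence to the blinded adjusters expressly so that unnecessary adjustments are avoided. There are reminder calls before TSH checks (Section 6.4), two-weekly calls (Section 6.7) and regular drug reconciliation (Section 5.9.3). A wrong step is capped at 25 mcg (LT4) or 8.3 mcg (LT3) per day, is followed by another TSH, and can be reversed by the reduction rows. Most of this stands and limits the weight of the point. What remains is that the calls are described as covering adverse events and symptoms, the only stated capsule return is at Visits 2 and 3, after that period's titration, and no section says how a TSH drawn after the supply ends is handled.

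A reader might also infer that the plan builds in a drug interruption. It does not: the gap needs a first check after week 6, no refill, and near-complete adherence, since missed doses stretch the supply.

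**Conclusion.** The point holds as a minor inconsistency between sections. Followed together, the stated supply, resupply trigger and window allow a first titration TSH up to 14 days after the capsules end (13 in period 1 if counted from Visit 1). At 14 days about 20-30% of LT4 and under 1% of LT3 would remain. The result could be an unneeded or larger capped increase and a longer titration, chiefly in period 2. In period 1 the error would usually be at most a difference between table rows.

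Two stronger readings are tempting and not supported. One is that the comparison of LT4 with LT3 is biased. Visits 2 and 3 still require a TSH at goal, and nothing in the documents shows an effect on TSH AUC, TSHmax, free T4, total T3 or bioactivity. The other is that participants typically face a 14-36% or 13-35% false increase. Those figures describe someone truly at goal on the period 1 starting dose, which is probably uncommon.

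The conclusion rests on full adherence, exactly 42 days supplied and no interim refill. Neither the number of late first checks nor the size of the TSH shift can be derived from the documents. The point covers only the first check in each period, because the size of later supplies is not stated.

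**What to change.** 1. Reconcile the starting supply and resupply timing (Sections 5.2, 5.4, 6.2, 6.5) with the accepted window in Section 6.4 and the four-week statements in Sections 3.1, 5.2 and 6.5. The sponsor decides which figure changes.
2. State in Section 6.4 whether the 4-8 week range applies to the first check in each period.
3. In Section 5.5, have the adherence report to the blinded adjuster include the last-capsule date whenever a titration TSH is drawn after the supplied days have run out. On-time draws need nothing extra.

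The cost is protocol wording and one recorded date for such draws, plus either tighter booking of first checks or up to 14 × 3 = 42 extra capsules per period (42/126 = 33% more) if the sponsor chooses to cover a week-8 draw. No extra participants, visits or procedures are needed.

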### **3.3 Secondary Study Endpoints**

The following endpoints will be measured at each study visit:

1. Unstimulated TSH bioactivity
2. Resting energy expenditure (REE) evaluation by indirect calorimetry
3. Weight
4. Body composition including body fat (percent and total), free fat mass, and bone density measured by dual energy x-ray absorptiometry (DXA)
5. Lipid profile via laboratory measurements
6. SF-36 for health status, hypothyroid symptoms (Appendix 2)
7. Heart rate and physical activity via actigraphy
8. Digit symbol substitution test
9. Body temperature using rectal temperature measurement
10. Optional exploratory genetic testing (one study visit only)
11. arterial tonometry, Doppler echocardiography, and arterial load assessment

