## **6 Study Procedures**

### **6.1 Screening Visit (Day -60 to Day -1)**

Upon arrival at the CTRC, the participant will review and sign the IRB-approved consent form. The participant will also review an optional exploratory genetics research study IRB-approved consent form and sign only if they agree to participate in the optional study. They will then be assigned a unique screening visit identification number. Participants will be asked for a thorough history detailing their past medical history, current medications, and social habits. They will perform the MMSE. The research nurse will measure weight, height, blood pressure, heart rate, and perform a 12 lead ECG. A study investigator will perform a physical examination. Subjects will have blood drawn to evaluate lab parameters for eligibility criteria. A free thyroxine (FT4) level in conjunction with a TSH level will be sent to confirm subclinical hypothyroidism. The thyroid stimulating hormone (TSH) test obtained during the screening visit is measured at least 4 weeks after the last elevated TSH. Instructions for use of the activity and heart rate monitors will be given to each participant. Participants will then be discharged to home. If participants are eligible for the study, an activity and heart rate monitor will be mailed to their home. Participants will be advised to wear the activity and heart rate monitor for 4 days) prior to the first study

CONFIDENTIAL

This material is the property of the University of Pennsylvania. Do not disclose or use except as authorized in writing by the study sponsor

visit. The heart rate band will be moistened with either water or gel per the activity monitor instructions. Participants will also be given a log to record when they place their heart rate and activity monitors on and off.

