## **6.6 Visit 3**

Participants will repeat all measures from Visit 2 at this final study visit on their second thyroid preparation (LT4 or LT3). The study will be complete.

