### 7.2 Statistical Methods

All statistical analyses will be performed under consultation with [name], Ph.D., a CTRC biostatistician. Our primary goal will be to assess changes in TRH stimulation test parameters at baseline compared to each thyroid hormone supplementation (LT4 or LT3) and our secondary goal will be to compare physiologic responses to LT4 and LT3 therapy from baseline. The area under the curve (AUC) for TRH-stimulated TSH response will be calculated using the trapezoidal rule. The maximum serum TSH concentration following TRH administration ( $TSH_{max}$ ) will be obtained by direct inspection of the serum concentration-time profiles. Changes in TSH bioactivity, free T4, and total T3 will be determined using the higher of the 120 or 180 minute post-TRH values. Paired t-tests will be used to examine change from baseline for each preparation, and two-tailed tests will be used to compare data between treatment arms. Nonparametric tests will be employed as needed. The primary outcomes will be the changes in TRH stimulation test parameters (AUC,  $TSH_{max}$ ,  $\Delta$  TSH bioactivity,  $\Delta$  free T4,  $\Delta$  total T3). Additional outcomes will include changes in unstimulated TSH bioactivity, REE, body temperature, weight, body composition, lipids, physical actigraphy and heart rate, cognitive testing, symptoms, arterial tonometry, and Doppler echocardiography.

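### Monitor wear is 4 days before Visit 1 but worded as one week before Visits 2 and 3, so change from baseline in activity and heart rate may compare unequal windows

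*Combined protocol and SAP*

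**What the plan says.** Section 3.3 lists, as one of eleven secondary endpoints measured at each study visit, "Heart rate and physical activity via actigraphy". Section 2 frames the secondary objectives as change between baseline and each thyroid preparation. Section 7.2 names these outcomes among the additional ones ("body composition, lipids, physical actigraphy and heart rate, cognitive testing, symptoms, arterial tonometry, and Doppler echocardiography") and uses paired t-tests for change from baseline on each preparation. The Study Summary gives no reference therapy, so Visit 1 is the only untreated comparator.

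The wear instructions are in two places:

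- Before Visit 1 (section 6.1): "Participants will be advised to wear the activity and heart rate monitor for 4 days) prior to the first study" visit.
- Before Visit 2 (section 6.4), after TSH reaches goal: "an activity and heart rate monitor will be mailed to the participant to wear one week prior to the next study visit".

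For Visit 3 there is no separate instruction. Section 6.5 says of the second period that "all study procedures for medication titration and TSH checks will be repeated as above", which brings in section 6.4, including its monitor sentence. Section 6.5 also says "Participants will repeat all measures from Visit 1 at this study visit on their first thyroid preparation (LT4 or LT3"), and section 6.6 makes Visit 3 a repeat of Visit 2. Neither states a wear time.

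Section 7.2 defines how the TRH-test summaries are derived. For actigraphy it does not say whether the summary is a daily mean or a total, and it sets no minimum number of valid days and no common window.

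**The concern.** Each participant's on-treatment value is compared with that participant's own baseline. If the baseline value comes from 4 days and the on-treatment value from 7, part of the observed change can come from which days were sampled. Four days before a weekday visit may hold no, one or two weekend days; seven days always hold two. With no untreated group, such a shift enters both drug-versus-baseline estimates in the same direction and cannot be separated from a drug effect. An activity total would also be larger over the longer window for no physiological reason. At stake is the interpretation of one secondary endpoint, not the primary TRH-test outcomes.

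**Working it through.** **The plan's own yardstick.** Section 7.1 gives a detectable change from baseline of 0.58 SD (alpha 0.05, 80% power, 30 enrolled, 15% dropout). Expected completers: 30 × 0.85 = 25.5. For a two-sided paired t-test (two-sided is assumed), power = P(T > t(0.975, n-1)), where T is noncentral t with n-1 degrees of freedom and noncentrality d√n. Setting this to 0.80 gives d = 0.584 for n = 25 and d = 0.572 for n = 26. The stated figure reproduces. It serves below only as a scale.

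**Inputs.** From the protocol: 4 days before Visit 1; one week before Visits 2 and 3, taken here as 7 days of wear. Assumed, because the documents do not say: visits fall Monday to Friday and are spread evenly, wear ends the day before the visit, and weekend and weekday levels differ by X.

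**Weekend share.** Over 7 days it is always 2/7 = 0.286. For the 4 days before Visit 1, with share s:

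| Visit 1 on | Days worn | Weekend days | s | 2/7 - s |
|---|---|---|---|---|
| Monday | Thu-Sun | 2 | 0.50 | -0.214 |
| Tuesday | Fri-Mon | 2 | 0.50 | -0.214 |
| Wednesday | Sat-Tue | 2 | 0.50 | -0.214 |
| Thursday | Sun-Wed | 1 | 0.25 | +0.036 |
| Friday | Mon-Thu | 0 | 0.00 | +0.286 |

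**Shift in change from baseline, using daily means.** For one participant the shift is (2/7 - s)X, from -0.21X to +0.29X. For the group, the mean of s is (0.50 + 0.50 + 0.50 + 0.25 + 0)/5 = 0.35, so the mean shift is (0.286 - 0.35)X = -0.064X.

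The documents give no value for X. Over a range, in SD of the change:

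| X | Individual shift | Group mean shift |
|---|---|---|
| 0.25 | -0.05 to +0.07 | -0.016 |
| 0.5 | -0.11 to +0.14 | -0.032 |
| 1.0 | -0.21 to +0.29 | -0.064 |

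Even at X = 1.0 SD the group shift is 0.064/0.58 = 11% of the detectable change. It would be larger only if Visit 1 clustered on certain weekdays: -0.21X if all fell Monday to Wednesday, +0.29X if all fell on Friday.

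**Precision.** With independent days and day-to-day variance σ², the error variance of the mean is σ²/4 at baseline and σ²/7 at follow-up, a ratio of 7/4 = 1.75.

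**Totals.** If activity were summed instead of averaged, equal daily activity would still give 7/4 = 1.75 times the baseline value.

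**LT4 against LT3.** For a participant with both on-treatment visits, (LT4 - baseline) - (LT3 - baseline) = LT4 - LT3. The baseline cancels, and both on-treatment values are collected under the same wording.

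**The case against.** The strongest objection is that section 6.4 may not set a duration at all. Section 6.1 says for how long; section 6.4 can be read as saying when. On that reading, the repeat of Visit 1 measures in section 6.5 could carry the 4 days forward, and none of the 7-day arithmetic applies. This stands as a limit on the size. It does not remove the inconsistency, because section 6.4 would then give no duration and the repeat instruction mentions no wear time.

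Section 6.1 also has a closing bracket with no opening one next to the 4-day figure, so words may have been lost there in editing or in conversion. The figure itself is legible, and no other section gives a different baseline duration.

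A reader might infer that the windows build a systematic bias into both drug-versus-baseline results. The documents do not support that. The individual shift changes sign with the weekday of Visit 1, the group average is small if visits are spread over the week, and neither X nor the visit-day pattern is given. Nor is the 1.75 variance ratio evidence of bias: unequal precision at the two time points does not invalidate a paired t-test.

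The damage can also be partly repaired. Section 6.1 provides a log of when monitors go on and off, so a longer follow-up record could be cut to a common number of days. No section prespecifies this.

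**Conclusion.** The two wear instructions do not match, and the plan does not reconcile them. Under the more natural reading, change from baseline in actigraphy heart rate and activity compares 4 days with 7. If daily means are used and visits are spread evenly over weekdays, the expected group shift is about -0.06X, small against the 0.58 SD the trial is sized to detect, with individual shifts from -0.21X to +0.29X adding noise. An activity total, which the plan does not rule out, would be seriously distorted. These sizes depend on the stated assumptions about visit days, the end of wear and seven-day follow-up wear. The extension to Visit 3 is inferred from section 6.5.

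It would go too far to conclude that the LT4-versus-LT3 comparison is compromised, since it shares one wear instruction and the baseline cancels. This is a minor, avoidable non-comparability in one secondary endpoint.

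**What to change.** State one wear duration and one timing relative to the visit, in both 6.1 and 6.4, for all three visits. A full week at each visit is the simpler choice because it also equalises the weekday/weekend mix. In section 7.2, define the summary as the mean per valid day, with a minimum number of valid days. Where baseline data have already been collected over 4 days, prespecify a common number of valid days to be used at each visit.

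The cost is a sentence in each section and three extra days of baseline wear, with no added visits or equipment. Visits should not have to be scheduled to match weekday mix: that would constrain all three visits for little gain.
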